3.3 Rationale for selecting Crisaborole (2%) ointment

In two phase-3 clinical studies, twice daily treatment with crisaborole (2%) ointment for 4 weeks was found to be an efficacious and well-tolerated treatment for mild-moderate atopic dermatitis/eczema (AD) when compared to no treatment. To aid clinical decision-making in the treatment of mild-moderate AD a comparison between the local effects of crisaborole (2%) ointment and a potent TCS on the skin is required. As a new topical anti-inflammatory and nonsteroidal treatment for AD, with no reported TCS-like local adverse effects, crisaborole is the ideal comparator for TCS in the development of new safety biomarkers.

Aim of this study: To determine the relative local skin effects of crisaborole (2%) ointment compared to a potent and moderately potent TCS in participants with AD. The focus is on ‘early biomarkers’ of ‘local skin changes’, and not clinical efficacy, which has been established in previous trials.

- **Research Question 3:** Does crisaborole (2%) ointment, cause skin barrier damage and epidermal atrophy, and if so how does it compare with a potent and moderately potent TCS?

Crisaborole (2%) ointment will be compared to the potent TCS, Betamethasone valerate 0.1% cream, in this study and to the moderately potent TCS Betamethasone valerate 0.025% cream in a subsequent study.

There is the potential that in the absence of atrophic effects crisaborole (2%) ointment will exert a positive additional benefit on the skin (promotes healthy skin barrier) associated with the specific topical formulation being tested. The base (vehicle) contains ingredients other than the active, including but not limited to petrolatum and butylated hydroxytoluene (BHT), that have the potential to independently (from the active) promote a healthy skin barrier. As such any effect reported could only be associated with the complete preparation under investigation (i.e. active combined with base) and could not be generalized to any other topical preparation containing crisaborole. The biomarkers of skin barrier structure (FTIR-based) may therefore provide additional information on AD related positive treatment effects, in addition to the presence or absence of negative effects, that can be explored within the remit of this study (as part of research question 2).

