3.5 Hypothesis

- Treatment with a potent TCS induces atrophic changes (reduced epidermal thickness determined by structural OCT) not observed with comparable crisaborole (2%) ointment treatment.
- Angiographic OCT measurements provide a robust and accurate biomarker of epidermal thickness/atrophy.
- FTIR spectra of the skin provide a biomarker of skin barrier structure that relates to skin barrier function and dysfunction, making it suitable for assessing both the negative effects of TCS and the positive effects of treatment bases/emollients.

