	filaggrin breakdown products) levels at the end of treatment	samples collected on day 29 using HPLC.
Exploratory objectives: To investigate whether OCT-derived biomarkers (other than the established structural OCT biomarker) enable the accurate quantification of tissue changes (vascular and matrix) associated with epidermal atrophy in response to TCS treatment	Exploratory outcomes: The difference in the change in superficial plexus depth (μm) measured by angiographic OCT The difference in the change in mean blood vessel diameter (μm) measured by angiographic OCT The difference in the change in blood vessel density (segments/mm ²) measured by angiographic OCT The difference in the change in collagen matrix index (an index derived from birefringence images of collagen density and arrangement) measured by polarisation sensitive (PS)-OCT	Angiographic OCT images taken on day 1, day 15, day 29 and day 57 Polarisation sensitive (PS)-OCT images taken on day 1 and day 29.
To investigate whether FTIR spectroscopy-derived biomarkers enable the accurate quantification of skin barrier condition and function in response to TCS treatment	The difference in the change in carboxylate levels (indirect measure of NMF levels, not to be confused with direct quantification from stratum corneum samples by HPLC) in the stratum corneum measured by FTIR spectroscopy The difference in stratum corneum lipid structure measured by FTIR spectroscopy in conjunction with tape-stripping	FTIR spectrum of the skin surface taken on day 1 day 15, day 29 and day 57 FTIR spectra taken through the stratum corneum (during tape-stripping) on day 29
To investigate the number of participants with FLG loss-of-function mutations and explore if there is any evidence of a relationship to treatment effects	Number of FLG loss-of-function mutation carriers Descriptive tabulations of TEWL and epidermal thickness by mutation status, if sufficient participants with mutation are detected.	Saliva sample at visit 1 for FLG genotyping TEWL and structural OCT derived epidermal thickness measured at day 1, day 15 and day 29

To identify (by completing the objectives above) a panel of biomarkers that best characterises epidermal atrophy. The biomarkers identified will be taken forward into the next stage of the research program.	All the above	Not applicable
--	---------------	----------------

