10.4.4 Exploratory outcome analysis

The primary and secondary analyses will identify where there is evidence of a difference between crisaborole ointment and betamethasone valerate cream in the change from baseline and which biomarkers are able to identify this difference in the clinical trial setting.

The exploratory analysis will investigate whether a sub set of the OCT endpoints can be used to non-invasively identify skin changes. This analysis will use multiple logistic regression to determine which of the new biomarkers provide the most informative and sensitive data pertaining to the atrophic changes induced by TCS treatment. This will be accomplished by assessing the ability of each biomarker to differentiate the skin of participants before and after treatment with the potent TCS, which is known to induce sub-clinical atrophic skin changes within the treatment window.

The biomarker (or subset of biomarkers) which are identified by this analysis will also be recorded in a subsequent study comparing crisaborole to a moderately potent TCS. This will enable the confirmation of the ability of the biomarkers to identify skin changes in a second independent dataset.

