To investigate whether OCT-derived biomarkers (other than the established structural OCT biomarker) enable the accurate quantification of tissue changes (vascular and matrix) associated with epidermal atrophy in response to TCS treatment. Biomarker measurements from the images will include:

- Superficial plexus depth (μm) from angiographic OCT images
- Mean vessel diameter (μm) from angiographic OCT images
- Vessel density (segments/ mm^2) from angiographic OCT images
- Collagen matrix index from polarisation sensitive OCT images

To investigate whether FTIR spectroscopy-derived biomarkers enable the accurate quantification of skin barrier condition and function in response to TCS treatment. Biomarker measurements from the spectra will include:

- NMF levels in the skin
- Lipid Structure

To investigate the number of participants with FLG loss-of-function mutations and explore if there is any evidence of a relationship to treatment effects.

To identify (by completing the objectives above) a panel of biomarkers that best characterises epidermal atrophy.

5. Analysis Sets and Protocol Deviations

Full Analysis Set (FAS): All subjects who were randomised into the study.

Per-protocol set (PPS): All participants who are deemed to have no major protocol violations that could interfere with the objectives of this study. This is a sub-population of the FAS.

Safety set: All randomised participants who receive at least 1 dose of test or reference cream.

All efficacy analyses and summaries will be performed on the FAS. If there are concerns about protocol deviations at the blind review, then a sensitivity analysis of the primary objective may be performed on the PPS.

Safety summaries will be performed on the safety set.

Prior to unblinding, a blind review of the data will be performed. The objective of the review is to identify protocol deviations and data queries and to make decisions regarding data analytical issues under blind conditions. Important violations of eligibility criteria and other deviations from the protocol will be assessed in cooperation with the study team. Important deviations from the protocol may lead to exclusion of a participant from the PPS. All deviations will be discussed and agreed prior to the unblinding of the data.

6. Endpoints and Covariates

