7.3 Exploratory Analysis

Discriminant analysis will be used to determine which of the new biomarkers provide the most informative and sensitive data pertaining to the atrophic changes induced by TCS treatment. This will be accomplished by assessing the ability of each biomarker to differentiate the skin of participants before and after treatment with the potent TCS, which is known to induce sub-clinical atrophic skin changes within the treatment window.

The endpoints that will be explored this way will be:

- Superficial plexus depth (µm) (day 1, day 15, day 29, day 57)
- Mean blood vessel diameter (µm) (day 1, day 15, day 29, day 57)
- Blood vessel density (day 1, day 15, day 29, day 57)
- Collagen matrix index (day 1, day 15, day 29, day 57)
- Carboxylate levels (day 1, day 15, day 29, day 57)
- Stratum corneum lipid structure (day 29)

Furthermore, summaries of the key outcomes (TEWL and epidermal thickness) by visit (day 1, day 15, day 29) will be made split by FLG loss-of-function mutation carriers.

Exposure and Compliance

A summary of the number of treatment days and the used weight per treatment day by treatment will be provided.

7.4 Adverse event data:

All Adverse Events will be summarized for all subjects enrolled in the study – both the number of participants with an AE and the total number of AEs. AEs will be tabulation by system organ class and by preferred term, as well as severity and relationship to treatment. Finally, those AEs which are specifically recorded as related to one of the test sites, the AEs will be summarised by test site. A listing, by participant number, will be produced to show the AEs at the worst severity and worst relationship to treatment.

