14.2.8 Superficial plexus depth (μm) (Full Analysis Set)
14.2.8.1 Change from baseline in superficial plexus depth (μm) (day 15 – day 1, day 29 – day 1, day 57 – day 1) (Full Analysis Set)

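### The biomarker panel is chosen only on before versus after betamethasone; no inferential comparison with the crisaborole forearm and no link to epidermal thickness is planned for the new markers.

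*SAP*

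**What the plan says.** **Aim of the panel.** SAP 4.3 seeks "a panel of biomarkers that best characterises epidermal atrophy", and Protocol 4.3 adds that the chosen markers go forward to the next stage of the programme. The second hypothesis in Protocol 3.5 is that "Angiographic OCT measurements provide a robust and accurate biomarker of epidermal thickness/atrophy".

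**Outcome definitions.** Protocol 4.7 words the exploratory marker outcomes as comparisons between treatments, for example "The difference in the change in carboxylate levels". The three angiographic measures and the collagen index are worded in the same way. Lipid structure is a between-treatment difference at day 29 only, and SAP 6.3 keeps it as a between-group endpoint.

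**Selection rule.** Protocol 10.4.4 and SAP 7.3 both judge each marker by "assessing the ability of each biomarker to differentiate the skin of participants before and after treatment with the potent TCS". The method differs. The protocol says "This analysis will use multiple logistic regression to determine which of the new biomarkers provide the most informative and sensitive data"; the SAP says "Discriminant analysis will be used to determine which of the new biomarkers provide the most informative and sensitive data". Neither gives a pass threshold.

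**Planned output.** SAP 7.1 and 7.2 model epidermal thickness, redness, TEWL, TEWL after tape-stripping, dryness and NMF. In SAP section 9 each of these has a table titled as an analysis. Tables 14.2.8 to 14.2.13 do not. Each gives a summary and a change table such as "Change from baseline in superficial plexus depth".

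**The concern.** A before/after change on the betamethasone forearm mixes the steroid effect with anything else that differs between day 1 and day 29. Protocol 6.3 requires a week without topical products on the test areas before day 1. The skin then receives a product twice daily for four weeks. Protocol 3.3 says of ingredients in the crisaborole base "that have the potential to independently (from the active) promote a healthy skin barrier", and Protocol 2.8.2 describes both products as having a petrolatum base. Season, handling and repeated measurement also fall in this interval.

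The trial has a randomised forearm in the same person that shares the time and washout effects, but the selection rule does not use it. Nor does it use epidermal thickness, the established measure of what the panel is meant to characterise. A marker unrelated to atrophy could rank well and be taken into the next study. A marker that tracks thickness closely would get no credit for doing so. The second hypothesis would end the trial untested.

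**Working it through.** **1. Is a between-forearm analysis of the new markers planned anywhere?**

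| Marker | Protocol 4.7 outcome | Modelled in SAP 7.1–7.2 | Rule in SAP 7.3 | Analysis table in SAP 9 |
|---|---|---|---|---|
| Plexus depth, vessel diameter, vessel density | difference in change | no | before/after TCS | none (14.2.8–14.2.10) |
| Collagen index | difference in change | no | before/after TCS | none (14.2.11) |
| Carboxylate | difference in change | no | before/after TCS | none (14.2.12) |
| Lipid structure | difference at day 29 | no | before/after TCS | none (14.2.13) |

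The opening of SAP section 7 says the primary and secondary analyses will show which biomarkers detect a treatment difference. Those analyses contain none of the markers above.

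Lipid structure, as defined, is measured during tape-stripping on day 29 only. It has no day-1 value, so the before/after rule cannot be applied to it. Table 14.2.13.1 nevertheless lists changes from day 1.

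**2. Is any marker related to epidermal thickness?** Thickness is neither in the SAP 7.3 marker list nor the reference for it. The interim plots in SAP 7.7 show thickness and carboxylate, but each endpoint is plotted separately. Protocol 7.7.6 says one scan supplies both structural and angiographic data, so the pairing needed is already there.

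**3. The plan's own figure.** Protocol 10.1 and SAP 2.3 use a difference of 3.55 µm, an SD of change of 5 µm, 80% power and 33 per group. SAP 7.5 sets a two-sided 5% level. With the noncentral t, power is 0.798 at 32 per group and 0.811 at 33, so 33 reproduces; 33/0.9 = 36.7, rounded up to 37. No figure is given for the panel analysis.

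**4. Illustration of a non-specific marker.** Assumptions: n = 33, two-sided 5% t-tests, and a shift of d (in SDs of the change) that is the same on both forearms. None of the shift sizes comes from the documents.

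- Before/after on one forearm: noncentrality d√n, 32 df, critical value 2.037. At d = 0.5 this is 0.5 × √33 = 2.87 and the rejection rate is 0.795. At d = 0.25 it is 0.29, and at d = 0.71 (3.55/5) it is 0.98.
- Between-forearm difference in change: the shared shift cancels, so the rejection rate is 0.05 at every d.

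**5. What the contrast costs for a real steroid effect.** For a betamethasone-only effect of 0.71 SD, the standardised difference is 0.71/√(2(1 − ρ)), where ρ is the correlation between forearms in the change. SAP 2.3 says the SD of this difference is unknown, so a range is shown: power is 80%, 90%, 98% and over 99% at ρ = 0, 0.25, 0.5 and 0.75.

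**6. Where the contrast alone misleads.** Suppose betamethasone leaves the marker unchanged and crisaborole ointment moves it by 0.5 SD. The standardised difference is 0.5/√2 = 0.354 at ρ = 0 and 0.5 at ρ = 0.5, so the contrast flags the marker in 50% and 80% of trials. If a change on the betamethasone forearm is also required, at most 5% can qualify, because that forearm rejects in only 5%. The same bound holds for the shared shift in step 4, through the contrast. For the real effect in step 5 the two conditions hold together in at least 0.977 + 0.799 − 1 = 78% of trials at ρ = 0.

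**7. Precision of a correlation with thickness.** For r = 0.3 and n = 33, Fisher's z = 0.310 with SE 1/√30 = 0.183. The 95% limits are 0.310 ± 0.358, which transform back to about −0.05 and 0.58.

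**The case against.** The best defence is that this is declared exploratory work. Protocol 3.4 calls the panel preliminary, and Protocol 10.4.4 plans confirmation in a second, independent dataset. Day-57 values are listed for most markers, and reversal after four weeks off treatment would argue against steady drift. This reduces the harm without removing it. Confirmation comes after selection, so it cannot recover a dropped marker. The SAP also does not say how day 57 enters the discriminant analysis, and reversal would not exclude a base effect.

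The simulated rates can fairly be called artificial, because the plan uses discriminant analysis with no threshold and the shift sizes are assumed. That stands, and they are offered only as illustration.

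It is also true that the between-forearm contrast is not a clean steroid effect. The two bases differ, there is no vehicle forearm, and step 6 shows that crisaborole or its base can drive the result. It should therefore not serve as the sole gate.

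Two stronger readings are tempting and fail. A reader might infer that the SAP swapped the protocol's contrast for a weaker one and failed to declare it in SAP 7.9. Protocol 10.4.4 already sets the same before/after rule, so there was no change of contrast to declare. The tension is inside the protocol, between 4.7 and 10.4.4. The move from logistic regression to discriminant analysis is a real change missing from SAP 7.9, but it is a separate matter. A reader might also infer that the crisaborole forearm is wholly unused for these markers. SAP 6.3 keeps a between-group lipid endpoint, and the blinded tables BDR8 to BDR13, split by location, suggest that the final tables may be split by treatment. The table shells are not shown, so what can be said is that no inferential comparison is listed.

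**Conclusion.** The point holds in a limited form. The panel is selected on a one-forearm before/after rule. The between-treatment outcomes in Protocol 4.7 have no planned inferential analysis for the angiographic, PS-OCT and carboxylate markers. Lipid structure has an endpoint but no analysis table, and it cannot be judged by the stated rule. The link to epidermal thickness, on which the second hypothesis and the panel objective rest, is not examined.

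The consequence is that a non-specific marker could rank highly, not that one will. The illustrative size is about 80% against 5% for an equal shift of 0.5 SD on both forearms, with 33 participants and a 5% t-test standing in for a criterion the SAP leaves open. The primary analysis is unaffected. This is an inexpensive improvement to an exploratory analysis that uses data the trial already collects.

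**What to change.** **In SAP 7.3 and tables 14.2.8 to 14.2.13:**

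- For each marker with a day-1 value, add the within-participant betamethasone minus crisaborole difference in change from day 1 to day 29, with a 95% CI.
- For lipid structure, add the day-29 between-forearm difference with a 95% CI, and take it out of the before/after rule.
- Show these beside the before/after result and each forearm's own change.
- For markers with a day-1 value, state that a marker is read as TCS-related only when the betamethasone forearm itself changes and the contrast agrees.
- Add, as descriptive only, the within-participant association with CI between each marker's between-forearm difference and the corresponding difference in epidermal thickness change. At r = 0.3 the interval in step 7 includes zero, so this cannot act as a gate.

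**Cost.** SAP wording and about one table per marker, with no new measurements or visits.

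**Downside, to be stated in the SAP.** The contrast removes shared time and washout effects but not base effects. It can be driven by crisaborole or its base. It will understate markers that both products move in the same direction, which is why the before/after result should stay beside it.

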7.5 Multiplicity considerations

All analyses in this SAP will be carried out with a two sided 5% significance level.

Secondary analyses are considered to be exploratory and so no adjustment will be made for multiplicity.

7.6 Missing and unusual data

Missing data will not be replaced. If appropriate the drop out rate will be calculated and analysed.

During data review (prior to data base lock and unblinding), readings that are incorrect, i.e. outside the equipment measurement range, will be removed. However, all readings that are possible, even if they are unusually low or high, will be kept in the analysis.

7.7 Interim Analysis:

[figure not shown]
It is of interest to review the data at an interim point to assess the ability of key biomarkers (epidermal thickness and Carboxylate levels) to detect any thinning of the skin over the first 4 weeks of the study. In order to explore this data without breaking the blind or introducing unplanned statistical analysis the following graphical approach is proposed:

For each patient with complete data, the change from baseline to day 29 will be calculated (for left and right arms separately). All the available data will be displayed together and no attempt will be made to identify which observations are related to each treatment. For each endpoint of interest the observations will be ordered according to size and plotted (see example below). This plot will allow clinical interpretation of the raw data to give an early indication of the magnitude of change in skin thickness that is being observed and the variation in that change.

A similar plot of the change from day 29 to day 57, with the observations ordered in the same way, will allow an early look at the recovery of the skin once treatment ends.

A further analogous plot showing skin barrier integrity (TEWLts20) after 28 days treatment will also be created.

Each bar in the plot represents the observation from a single arm, thus each patient will contribute two bars but these will not be linked in the plot.

7.8 Data Monitoring Committee (DMC):

No DMCs are planned for this trial.

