4.5 Secondary endpoint/outcome

- The difference in the change in epidermal thickness measured by structural OCT during and after 28 days treatment. OCT images of epidermal thickness taken on day 1, day 15, day 29 and day 57.
- The difference in the change in skin redness/erythema (relating to tolerability) during and after 28 days treatment determined by:
 - Visual redness/erythema score determined on day 1, day 15, day 29 and day 57
 - Objective redness assessed with the Mexameter measured on day 1, day 15, day 29 and day 57
- The difference in the change in Trans-Epidermal Water Loss (TEWL, relates to skin barrier function) during and after treatment.^{17,18} TEWL measurements on day 1, day 15, day 29 and day 57.
- The difference in skin barrier integrity (TEWL_{t=20}) after 28 days treatment. TEWL measurements after tape-stripping (TEWL_{t=20}) on day 29
- The difference in the change in visual skin dryness during and after treatment. Visual skin dryness scored on day 1, day 15, day 29 and day 57
- The difference in Natural Moisturising Factor (NMF, filaggrin breakdown products) levels at the end of treatment¹⁹ NMF will be quantified from superficial stratum corneum samples collected on day 29 using HPLC.

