7.7.2 Identification and demarcation of the test sites

The test/treatment sites are located on the volar side of the forearm (Figure 7.1). There are 2 treatment areas in total, one on each forearm. Within each treatment area there are 2 defined test or measurement areas. Before performing any skin assessments, during the acclimatization period, the test areas should be marked out discretely using a ruler, and skin marking pen with the help of the guide below. The table lists the measurements performed at each test area in the order they should be collected.

Figure 7.1: The location of the treatment areas and test sites**Table 7.3:** The measurements to be performed at each test site

Test area	Measurement
R1/2 (combined), L1/2 (combined)	
 1. Visual scoring of skin dryness and redness at each test site
R1, L1	
 2. Capture of 2D skin image using the c-cube 3. Mexameter measurement at each site (skin redness, 4 repeats) 4. OCT (structural & angiographic) image capture at each site (in triplicate) 5. PS-OCT image capture at each site (in triplicate) 6. TEWL measurement at each site (in duplicate) 7. FTIR spectrum from the skin surface collected at each site
R2, L2	
 2. Capture of 2D skin image using the c-cube 3. Mexameter measurement at each site (skin redness, 4 repeats) 4. TEWL measurement at each site (in duplicate) 5. FTIR spectrum from the skin surface collected at each site 6. Tape-stripping in conjunction with TEWL and FTIR (to achieve full stratum corneum depth) 7. Tape-strip sample collection

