7.7.10 Tape-stripping in conjunction with FTIR and TEWL measurements

Tape-stripping, to study deeper layers of the stratum corneum, involves the repeated application and removal of D-Squame cutaneous stripping discs (CuDerm cooperation, Dallas, USA) to/from the skin in a standardised manner.^{16,34} A specially designed plunger is used to exert a standardised pressure (225g/cm²) to each disc. Approximately 3 corneocyte layers (incomplete layers/uneven coverage) are removed per disc, depending on the volunteer and the treatment conditions. This enables measurements of deeper layers of the skin to be collected by TEWL machine or FTIR spectroscopy.

Tape-stripping will be performed on day 29 only, once within each treatment area (test sites R2 and L2). At each site 20 consecutive tape-strippings will be performed. The depth through the stratum corneum is determined by measuring the amount of corneocytes removed by each disc using the SquameScan Device. Squamescan readings of each tape should be collected in triplicate. The tape-strips, containing a sample of the stratum corneum, will be collected as outline below.

In conjunction with tape-stripping, FTIR spectra and TEWL measurements (single) will be collected from the tape-stripped site after every 5 consecutive tape-strips as described above. This data is used to determine the lipid structure throughout the stratum corneum.

After the 20th tape-strip and final FTIR measurement, a single TEWL measurement should be collected, as described above. This is taken to determine stratum corneum integrity (skin barrier function following experimental barrier perturbation). The parameter is referred to here as TEWL_{ts20}

Further details on performing tape-stripping can be found in SOP-021.

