7.2 Secondary Analysis

The analysis of three of the secondary endpoints will use a repeated measures mixed model with change from day 1 (to day 15, day 29, day 57) as the outcome, treatment, timepoint as factors together with a treatment by timepoint interaction, subject as a random effect and baseline as a covariate.

The model will be used to estimate the difference between treatment arms for the change from baseline to day 29.

If there is a significant difference observed in the change from baseline to day 29, then the change from day 1 to day 15, and the change from day 29 to day 57 will also be assessed. If there is no statistically significant difference in the change from baseline to day 29 then we will not test further timepoints.

Summary statistics will be presented for all timepoints.

This applies to:

- Change in epidermal thickness (change from day 1 to day 15, and from day 29 to day 57 as secondary endpoints)
- Change in redness/erythema
- Change in Trans-Epidermal Water Loss (TEWL)
- Change in visual skin dryness

The Change in TEWL_{ts20} after 28 days treatment will use an ANCOVA model with change from day 1 to day 29 as outcome, treatment as a factor, subject as a random effect and baseline as a covariate. The analysis of Natural Moisturising Factor after 28 days treatment (day 29) will

use a paired analysis (such as a t-test, depending on the distribution of the data) unless it is necessary to adjust for any covariates, in which case an ANCOVA will be used. If any of the above models do not fit satisfactorily or appear to be over fitted the analysis may be changed to look at change from baseline to day 29 and change from day 29 to 57 separately.

Since these analyses are exploratory, no adjustment for multiplicity will be made.

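### SAP 7.6 treats any reading outside the instrument range as an error and deletes it, so a true off-scale TEWLts20 (or, if the rule extends to HPLC, NMF) value would be lost in an outcome-dependent way; the harm is conditional and minor

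*SAP*

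**What the plan says.** SAP 7.6 sets the data-handling rule for every endpoint. At the review before database lock and unblinding, "readings that are incorrect, i.e. outside the equipment measurement range, will be removed". The following sentence adds that "all readings that are possible, even if they are unusually low or high, will be kept in the analysis". The section also states that "Missing data will not be replaced".

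Two secondary endpoints have no replicate behind them:
- **TEWLts20.** Protocol Table 7.3 lists "Tape-stripping in conjunction with TEWL and FTIR (to achieve full stratum corneum depth)" at sites R2 and L2. Protocol 7.7.10 then says "After the 20th tape-strip and final FTIR measurement, a single TEWL measurement should be collected", and that "Tape-stripping will be performed on day 29 only". SAP 7.2 analyses it by ANCOVA with a random subject effect.
- **NMF.** Protocol 4.5 says "NMF will be quantified from superficial stratum corneum samples collected on day 29 using HPLC". SAP 6.4 takes one sample from each side. SAP 7.2 uses a paired analysis by default, with the test chosen by the distribution, and ANCOVA if covariates are needed.

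Neither document states the TEWL instrument's range, an HPLC quantification limit, or how to handle a value beyond either.

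**The concern.** A reading beyond an instrument's range can be a fault, or it can be a true value known only to be at least (or at most) the limit. The SAP's definition of an incorrect reading covers both.

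The distinction matters because of the direction of damage. In the preliminary data of Protocol 2.3, TEWL with tape-stripping was higher on betamethasone than on tacrolimus (Figure 2.5, p = 0.0024). The NMF components PCA and UCA were lower on betamethasone than in untreated skin (Figure 2.6). A TEWLts20 value above range or an NMF value below quantification would therefore tend to come from the betamethasone forearm of a badly affected participant. Removing it depends on the outcome, and through the outcome on treatment. In a comparison meant to show local harm, the bias runs toward hiding it.

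**Working it through.** **1. The plan's own figure.** Sample size is stated only for the primary endpoint: difference 3.55 µm, SD 5 µm, two-sided 5%, 80% power, 33 per group on a parallel-group basis. The normal approximation gives n = 2(1.960 + 0.842)² × 5² / 3.55² = 31.1, so 32. With the t distribution, power is 79.8% at 32 and 81.1% at 33, so 33 is reproduced. Recruitment: 33 / 0.9 = 36.7, so 37. This fixes the number of pairs. It gives no SD, difference or range for TEWLts20 or NMF.

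**2. Assumptions for the illustration.** 33 pairs; normal arms with unit SD; true difference d = 0.71 (borrowed: 3.55 / 5) or 0.50; between-arm correlation ρ = 0, 0.5 or 0.8; a share q of betamethasone readings above a limit c, with c = d + z(1−q). The same limit applies to both arms. By symmetry, a lower limit for NMF gives the same results.

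**3. Closed form at ρ = 0.** With independent arms, the difference left after complete-pair deletion is d − φ(c−d)/Φ(c−d) + φ(c)/Φ(c). For q = 20%, c − d = 0.842 and the first ratio is 0.2800 / 0.80 = 0.350.
- d = 0.50: c = 1.342, second ratio 0.1622 / 0.9101 = 0.178. Left: 0.50 − 0.350 + 0.178 = 0.328, or 66%.
- d = 0.71: c = 1.552, second ratio 0.1197 / 0.9396 = 0.127. Left: 0.71 − 0.350 + 0.127 = 0.487, or 69%.

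**4. Simulation** (20,000 trials per cell, paired t-test). Limit columns show off-scale values kept at the limit.

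| d (SD) | ρ | off scale | difference kept, deletion | power, deletion | difference kept, limit | power, limit |
|---|---|---|---|---|---|---|
| 0.71 | 0 | 0% | 100% | 0.80 | 100% | 0.80 |
| 0.71 | 0 | 3% | 92% | 0.75 | 99% | 0.80 |
| 0.71 | 0 | 10% | 81% | 0.65 | 95% | 0.79 |
| 0.71 | 0 | 20% | 69% | 0.51 | 88% | 0.78 |
| 0.71 | 0.5 | 10% | 90% | 0.94 | 95% | 0.97 |
| 0.71 | 0.5 | 20% | 83% | 0.88 | 88% | 0.97 |
| 0.71 | 0.8 | 3% | 98% | 1.00 | 99% | 1.00 |
| 0.71 | 0.8 | 10% | 95% | 1.00 | 95% | 1.00 |
| 0.71 | 0.8 | 20% | 92% | 1.00 | 88% | 1.00 |
| 0.50 | 0.5 | 0% | 100% | 0.79 | 100% | 0.79 |
| 0.50 | 0.5 | 10% | 88% | 0.68 | 94% | 0.78 |
| 0.50 | 0.5 | 20% | 81% | 0.57 | 86% | 0.76 |

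The largest power loss is 0.80 − 0.51 = 0.29. At ρ = 0.8 and d = 0.71 there is none. For d = 0.50 and ρ = 0.5, a Wilcoxon signed-rank test on limit values gives power 0.77 and 0.75 at 10% and 20% off scale (3,000 trials).

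**5. TEWLts20 under a random-subject model.** The remaining forearm stays in this analysis. With d = 0.71 and 10% off scale (300 runs, no baseline term), it keeps 83%, 86% and 92% of the difference at ρ = 0, 0.5 and 0.8. Complete pairs in the same runs keep 83%, 91% and 96%. Retaining the other arm does not remove the attenuation.

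**The case against.** The strongest reply is that no trigger is shown. No range or quantification limit is given, and the preliminary study reports both measures at n = 25 with no hint of lost values. This stands. A reader might infer that off-scale readings will occur, or that bias is established; the documents support neither.

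A reader might also infer that one deleted reading always drops the participant. That fits NMF under its default paired analysis. It does not fit TEWLts20, where the other forearm can stay in the model, although the attenuation persists. (Separately, that ANCOVA asks for a day 1 TEWLts20 value that is never collected.)

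Applying the rule to NMF is an interpretation: an HPLC quantification limit need not be part of an equipment range. If the rule does not apply, the SAP has no rule for unquantifiable NMF.

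The sentence keeping possible readings can be read as limiting deletion to absurd entries. Because the preceding sentence defines incorrect by range, a true off-scale value is claimed by both. The text is at best ambiguous.

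There are real safeguards. Removal is blinded, Protocol 10.3 has summaries show the amount of missing data, and a rank test is already open for NMF. Blinding prevents selective removal, but this rule acts on the outcome itself. Counting losses does not restore them, and no test can use a deleted value.

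**Conclusion.** The point holds as a conditional wording gap of minor severity. As written, the rule would remove true values beyond the limit, mostly from the more damaged arm, and bias two secondary comparisons toward no difference. SAP 7.5 treats the secondary analyses as exploratory. The primary endpoint, a mean of triplicate OCT readings, is not at issue.

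The size rests wholly on assumed inputs. Across the ranges in the working, deletion keeps about 66-98% of the true difference and costs 0 to about 30 points of power. The loss is large only when many readings are off scale and the two arms are weakly correlated. At correlation 0.8, limit values recover no more of the mean difference than deletion does at 10% off scale, and less at 20%. With no off-scale reading there is no effect.

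**What to change.** Amend SAP 7.6 before unblinding:
- State each instrument's range and the HPLC quantification limit, and say whether the rule covers HPLC.
- Remove a reading only if it is physically impossible or has a documented instrument, operator or entry fault.
- Keep a true above-range or below-quantification value as censored: record it at the limit and flag it.
- If any occur, analyse that endpoint with a censored-data model or a paired rank-based method (for example, Wilcoxon signed-rank with the Hodges-Lehmann estimate).
- Report the number of such values per treatment.

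The cost is a few lines of SAP text; no data collection changes. The downside is that values set at the limit still understate the mean difference (88% kept at 20% off scale with d = 0.71), so the mean should not be the only estimate when they occur.
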